10.5.3 Safety objectives

10.5.3.1 Analysis set and grouping for the analyses

For all safety analyses, the safety set will be used. All listings and tables will be presented by treatment arm.

The overall observation period will be divided into three mutually exclusive segments:

- 1. pre-treatment period: from day of subject's informed consent to the day before first dose of study medication
- 2. on-treatment period: from day of first dose of study treatment to 130 days after last dose of study treatment
- 3. post-treatment period: starting at day 131 after last dose of study treatment.

10.5.3.2 Adverse events (AEs)

Summary tables for adverse events (AEs) will include only AEs with onset date during the ontreatment period, the treatment-emergent AEs.

The incidence of treatment-emergent adverse events will be summarized by system organ class and or preferred term, severity (based on CTCAE grades), type of adverse event, and relation to study treatment.

Serious adverse events, non-serious adverse events and adverse events of special interest (AESI) during the on-treatment period will be tabulated. AESIs will be defined based on the current case retrieval strategy (CRS).

All reported deaths (on-treatment and post-treatment) will be summarized.

All AEs, deaths and serious adverse events (including those from the pre and post-treatment periods) will be listed and those starting during the pre-treatment and post-treatment period will be flagged.

10.5.3.3 Laboratory abnormalities

Grading of laboratory values will be assigned programmatically as per NCI Common Terminology Criteria for Adverse Events (CTCAE) version 5.0. The calculation of CTCAE grades will be based on the observed laboratory values only, clinical assessments will not be taken into account.

CTCAE Grade 0 will be assigned for all non-missing values not graded as 1 or higher.

For laboratory tests where grades are not defined by CTCAE 5.0, results will be categorized as low/normal/high based on laboratory normal ranges. If required, for certain laboratory parameter, values lower than lower limit of normal (LLN) or higher than upper limit of normal (ULN) may further be summarized into categories based on multiples of LLN or ULN respectively.

The following listings/summaries will be generated separately for hematology, and biochemistry tests:

• Listing of all laboratory data with values flagged to show the corresponding CTCAE v5.0 grades if applicable and the classifications relative to the laboratory normal ranges

For laboratory tests where grades are defined by CTCAE v5.0

- Worst post-baseline CTCAE grade (regardless of the baseline status). Each subject will be counted only once for the worst grade observed post-baseline.
- Shift tables using CTCAE v5.0 grades to compare baseline to the worst on-treatment value

For laboratory tests where grades are not defined by CTCAE v5.0

• Shift tables using the low/normal/high/ (low and high) classification to compare baseline to the worst on-treatment value.

In addition to the above mentioned tables and listings, other analyses if needed, for example figures plotting time course of raw or change in laboratory tests over time or box plots may be specified in the analysis plan.

10.5.3.4 Other safety data

ECG

Notable ECG data will be summarized by treatment. In addition, a listing of these subjects will be produced by treatment arm with notable values flagged.

Vital signs

Notable vital signs will be summarized by treatment. In addition, a listing of these subjects will be produced by treatment arm with notable values flagged.

10.5.3.5 Supportive analyses for secondary objectives

If the primary analysis on OS is statistically significant, subgroup analyses to assess the homogeneity of the treatment effect across demographic and baseline disease characteristics will be performed. The subgroups to be considered will be defined in the SAP.

10.5.3.6 Tolerability

Not applicable

10.5.4 Pharmacokinetics,

and immunogenicity

PAS will be used in the pharmacokinetic data analysis. Descriptive statistics (n, m (number of non-zero concentrations), mean, CV%, SD, median, geometric mean, geometric CV%, minimum and maximum) for canakinumab concentrations will be presented at each scheduled timepoint. For canakinumab, pre-dose concentrations collected before dose administration on Day 1 of Cycle 2 and beyond are Ctrough.

All concentration data for canakinumab vs. time profiles will be displayed graphically.

10.5.4.1 Data handling principles

Missing values for any PK parameters or concentrations will not be imputed and will be treated as missing.

Below the limit of quantitation (BLQ) values will be set to zero by the Bioanalyst, and will be displayed in the listings as zero and flagged. BLQ values will be treated as missing for the calculation of the geometric means and geometric CV%.

10.5.4.2 Population pharmacokinetic analysis

If there is adequate amount of data, a mixed-effects model may be applied to the serum canakinumab concentration-time data from this study along with other studies to generate posthoc estimates of pharmacokinetic parameters using NONMEM to characterize canakinumab exposure and to determine the effects of intrinsic (i.e. demographic factors) and extrinsic covariates (e.g. concomitant medications) on canakinumab exposure. If there is sufficient data for analysis, the details of the population pharmacokinetic analyses may be provided in a separate reporting and analysis plan, and the results may be reported in a separate population pharmacokinetic report.

10.5.4.3 Immunogenicity

Immunogenicity will be characterized descriptively by tabulating anti-drug antibodies (ADA) prevalence at baseline and ADA incidence on-treatment.

10.5.5 Resource utilization

Not applicable

10.5.6 Patient-reported outcomes

Three patient-reported outcomes (PRO) questionnaires will be assessed: EORTC QLQ-C30 with QLQ-LC13 incorporated and the EQ-5D-5L. QLQ-C30 and QLQ-LC13 will be considered as the primary scale. Scoring of PRO data and methods for handling of missing items or missing assessments will be handled according to the scoring manual and user guide for each respective subject questionnaire (Fayers 2001, Van Reenen 2015). No imputation procedures will be applied for missing items or missing assessments.

The FAS will be used for analyzing PRO data. Time to definitive 10 point deterioration symptom scores of pain, cough and dyspnea per QLQ-LC13 questionnaire are primary PRO variables of interest. Time to first 10 point deterioration symptom scores of pain, cough and dyspnea per QLQ-LC13 questionnaire, time to first 10 point deterioration of global health status/QoL, shortness of breath and pain per QLQ-C30 questionnaire, time to 10 point definitive deterioration of global health status/QoL, shortness of breath status/QoL, shortness of breath and pain per QLQ-C30 together with the utilities derived from EQ-5D-5L are secondary PRO variables of interest.

Confidential

[figure not shown]
Time to deterioration in symptoms and in global health status/QoL are defined as follows:

- The time to definitive 10 point deterioration is defined as the time from the date of randomization to the date of event, which is defined as at least 10 points absolute increase from baseline (worsening) of the corresponding scale score, with no later change below this threshold i.e. < 10 points was observed or if this increase was observed at the last assessment for the subject, or death due to any cause, whichever occurs earlier. If a subject has not had an event, time to definitive deterioration will be censored at the date of the last adequate assessment. The distribution will be presented descriptively using Kaplan-Meier curves. Summary statistics from Kaplan-Meier distributions will be determined, including the median time to definitive 10 point deterioration along with two-sided 95% confidence interval. Additionally, time to definitive deterioration with different definition for deterioration may be specified in the SAP as deemed appropriate. A stratified Cox regression will be used to estimate the hazard ratio (HR), along with two-sided 95% confidence interval.
- Thetime to first 10 point deterioration is defined as the time from the date of randomization to the first onset of at least 10 points absolute increase from baseline (worsening) in symptoms scores or at least 10 points absolute decrease from baseline (worsening) in global health status/QoL, or death due to any cause, whichever occurs earlier. If a subject has not had an event, time to deterioration will be censored at the date of the last adequate assessment. The distribution will be presented descriptively using Kaplan-Meier curves. Summary statistics from Kaplan-Meier distributions will be determined, including the median time to 10 point deterioration along with two-sided 95% confidence interval. Additionally, time to first deterioration with different definitions for deterioration may be specified in the SAP as deemed appropriate. A stratified Cox regression will be used to estimate the hazard ratio (HR), along with two-sided 95% confidence interval.

Descriptive statistics will be used to summarize the original scores, as well as change from baseline, of the QLQC30/QLQ-LC13 and EQ-5D-5L at each scheduled assessment time point for each treatment group. Additionally, change from baseline in the scale and subscale values at the time of each assessment will be summarized. Subjects with an evaluable baseline score and at least one evaluable post baseline score during the treatment period will be included in the change from baseline analyses.

The number of subjects completing each questionnaire and the number of missing or incomplete assessments will be summarized by treatment group for each scheduled assessment time point. No formal statistical tests will be performed for PRO data and hence no multiplicity adjustment will be applied. The FAS will be used for analyzing PRO data.

In addition, a repeated measurement analysis model will be used to compare the treatment groups with respect to changes in all domain scores of the EORTC QLQ-C30/QLQ-LC13 as well as the thermometer and utility scores of the EQ-5D-5L, longitudinally over time. The differences in least square means between the treatment arms and corresponding 95% confidence interval at selected time points will be presented. Details, including handling of missing data, will be specified in the SAP.

Confidential

10.7 Interim analysis

10.7.1 Disease free survival (DFS)

One interim analysis is planned after approximately 196 of the approximately 392 targeted DFS events (i.e., at approximately 50% information fraction) have been documented. The primary intent of the interim analysis is to stop early for lack of efficacy (futility). There is no intent to carry out an analysis to declare superior efficacy at the time of the interim analysis. An α -spending function according to a two-look (Lan-DeMets) group sequential design with (O'Brien-Fleming) type stopping boundary (as implemented in East 6.4) will be used to construct the efficacy stopping boundaries (Lan and DeMets 1983). A user-defined gamma function with γ =-3 stopping boundary as implemented in East 6.4 will be used as a β -spending function to determine the non-binding futility boundary. The choice of non-binding nature of the futility stopping boundary ensures that the efficacy stopping boundaries are not affected. Based on the choice of α -spending and β -spending function described above and if the interim analysis is performed exactly at 196 DFS events, the futility boundary expressed on the p-value

scale (or the Z-statistic scale) at the first interim is calculated as p = 0.411 (or Z = 0.226). The observed (i.e., nominal) p-value has to be greater than p-value scale futility boundary = 0.411 (or the observed Z-statistic has to be < Z-statistic scale boundary = 0.226) to conclude futility. Since the observed number of events at the interim analysis may not be exactly equal to the planned 196 DFS events, the futility boundary will need to be recalculated using the prespecified α and β -spending functions and based on the actual number of observed events at interim and the total number of targeted events to calculate the exact information fraction. The observed p-value (or Z-test statistic) at the interim analyses will then be compared against the re-calculated futility boundary.

If the study continues to the final DFS analysis, the final DFS analysis will be performed when approximately 392 DFS events have been documented. If exactly 196 events are observed at the interim analysis, the study continued and exactly 392 events are obtained at the final analysis, the observed p-value will have to be less than 0.024 (or the observed Z statistics has to be > 1.969) to declare statistical significance. In practice, the final analysis will be based on the actual number of DFS events documented at the cut-off date for the final DFS analysis and α already spent at the interim analysis. The boundary for the final analysis will be derived accordingly from the pre-specified α -spending function such that the overall significance level across all analyses is maintained at 0.025.

The statistical properties of the group sequential design are summarized for DFS in Table 10-1 below.

Scenario	Look	# DFS events	Simulated cumulative probabilities (%)		Simulated incremental probabilities (%)	
			Stop for efficacy	Stop for futility	Stop for efficacy	Stop for futility
Under H ₀₁ (HR=1)	1st IA (futility)	196	-	59.34	-	59.34
	Final	392	2.36	-	2.18	-
Under H _{a1} (HR=0.716)	1st IA (futility)	196	-	1.83	-	1.83
	Final	392	89.56	-	63.7	-
Under HR=0.8	1st IA (futility)	196	-	9.28	-	9.28
	Final	392	58.65	-	50.49	-

Table 10-1Simulated probabilities to stop for futility or efficacy at the interim or
final DFS analysis

Note: Simulation is performed in East 6.4 with number of simulations = 10,000 and randomization seed = 1234

The interim analysis will be performed by an independent statistician (not involved with the conduct of the study). Further details will be described in the DMC charter. The results of the interim analysis will be provided to the DMC by the independent statistician.

10.7.2 Key secondary endpoint: Overall survival (OS)

A hierarchical testing procedure will be adopted and the statistical tests for OS will be performed only if the primary efficacy endpoint DFS is statistically significant.

A maximum of three analyses are planned for OS; at the time of the final analysis for DFS (provided DFS is statistically significant), at which point a total of approximately 318 (63%) deaths are expected, an additional IA for OS when a total of approximately 418 (83%) deaths are expected (expected 52 months from the date of the first subject being randomized), and a final analysis for OS when approximately 504 deaths are expected (expected 63 months from the date of the first subject being randomized).

An α -spending function according to Lan-DeMets (O'Brien-Fleming) as implemented in East 6.4 (Lan and DeMets 1983), independent of the one used for the DFS, along with the testing strategy outlined below will be used to maintain the overall type I error probability. This guarantees the protection of the 2.5% overall level of significance across the two hypotheses and the repeated testing of the OS hypotheses in the interims and the final analysis (Glimm 2010).

The trial allows for the stopping of the study for a superior OS result, provided the primary endpoint DFS has already been shown to be statistically significant favoring the test treatment arm. Further, the exact nominal p-values that will need to be observed to declare statistical significance at the time of these analyses for OS will depend on the number of OS events that have been observed at the time of these analyses and the α for OS already spent at the time of earlier analyses.

The projected timing of interim analysis is summarized in Table 10-2.

At the time of final DFS analysis, both DFS and interim OS analysis will be performed by the Sponsor's clinical team. Investigators and subjects will remain blinded to study treatment and all subjects will continue to be followed for OS until the final OS analysis (or earlier if OS reaches statistical significance at any of the interim analyses).

The statistical properties of the group sequential design are summarized for OS in Table 10-2 below.

Look	Months after randomization of the first subject (approximation)	# DFS Events	Cumulative power against a hazard ratio of 0.716	# OS Events	Cumulative power ^b against a hazard ratio of 0.776
1st DFS IA (futility)	27	196 (50.0%)	-	-	-
Final DFS	42	392 (100%)	89.56%	318 (63.1%) ^a	36.26%
OS IA	52	-	-	418 (82.9%) ^a	64.09%
Final OS	63	-	-	504 (100%) ^a	79.25%

Table 10-2Simulated cumulative power to stop for efficacy on overall survival at
final DFS analysis or final OS analysis

a: To be performed only if the final DFS analysis is significant

b: Power conditional on DFS being significant

Simulations performed in East 6.4 with number of simulations = 10,000 and randomization seed =1234.

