As of 03-Feb-2022, 1840 patients have been screened and 1382 patients have been randomized and treated in the CANOPY A trial. On 23-Apr-2021, the interim analysis of DFS related to futility was performed by independent Data Monitoring Committee (DMC) when 201 DFS events were documented on 01-Feb-2021. The trial was recommended to continue without modification. The last independent DMC review of the safety data from 1234 randomized patients (cut-off date 01-Sep-2021), and the serious adverse events (cut-off date 21-Nov-2021) took place on 12-Dec-2021. The DMC recommendation was that the study can continue without modifications.

The main purpose of this protocol amendment is to:

- Remove the second interim analysis for Disease Free Survival (DFS) originally planned
- Include the comparison between the canakinumab and placebo arms of DFS by investigator local assessment and OS in subgroups defined respectively by PD-L1 and CD8 expression as secondary endpoint.
- Add time to first 10 point deterioration for symptoms and global health status/QoL as a secondary patient-reported outcomes variable of interest
- Add disruption proofing language

Rationale for updating the interim analysis plan for DFS

The originally planned 2nd interim analysis of DFS in this event-driven trial was not performed since the pre-specified number of DFS for this interim analysis (294) had been reached before the planned 1500 subjects were randomized and did not have at least one post-baseline efficacy assessment, which is required by the protocol. As such all the relevant wording in section 4 and 10 are not applicable anymore and have been removed.

As per protocol, the final DFS analysis is planned to be performed when approximately 392 progression events have been observed and all enrolled subjects have a minimal efficacy followup of 3 months to ensure all subjects have at least one post-baseline recurrence assessment.

Per sponsor's decision, considering the projected number of DFS events approaching the target for the final DFS analysis the screening activities ended on December 7th, 2021. A total of 1382 subjects were randomized, which is less than 1500 subjects originally planned.

Rationale for including PD-L1 subgroup analysis as a secondary endpoint

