10.9 Power for analysis of key secondary variables

OS, as the key secondary variable, will be formally statistically tested, provided that the primary variable DFS is statistically significant. The hypotheses to be tested and details of the testing strategy are provided in Section 10.5.1 and Section 10.7.2. Based on available data, the median OS in the placebo arm is expected to be approximately 5 years (Pignon 2008). In addition, the OS result presented in Kelly (2015) was not mature as the median was not reached at 5 years, but the overall trend indicates a median OS greater than 5 years. After taking these into consideration, the median OS for the placebo arm is assumed to be approximately 66 months. It is hypothesized that treatment with canakinumab will result in a 22.4% reduction in the hazard rate for OS, i.e., an expected hazard ratio of 0.776 (which corresponds to an increase in median 66 to 85 months under the exponential model assumption). Then, in order to ensure 80% power to test the null hypothesis: OS hazard ratio = 1, versus the specific alternative hypothesis: OS hazard ratio = 0.776, it is calculated that a total of 504 deaths need to be observed. This calculation assumes analysis by a one-sided log-rank test at the overall 2.5% level of significance, subjects randomized to the two treatment arms in a 1:1 ratio, and a 3-look group sequential design with a Lan-DeMets (O'Brien-Fleming) a-spending function using information fractions of 63%, 83% and 100%. Based on the same number of subjects that are planned to be enrolled in this study to provide sufficient power for the primary endpoint (i.e., 1500 subjects), and assuming losses to follow-up for OS of 3% yearly, it is estimated that these 504 deaths will be observed approximately 63 months after the randomization date of the first subject. Therefore the cut-off date for the final analysis of OS will be approximately 21 months

after the cut-off date for the final analysis of DFS. These calculations were made using the software package East 6.4.

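### The OS powers in Table 10-2 are stand-alone figures mislabelled as conditional on DFS, and the roughly 73–78% chance of a formal OS success is not reported

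*Protocol*

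**What the plan says.** Protocol 10.9 sizes the key secondary endpoint "in order to ensure 80% power to test the null hypothesis: OS hazard ratio = 1", with "an expected hazard ratio of 0.776" and a "one-sided log-rank test at the overall 2.5% level of significance". It adds that "the median OS for the placebo arm is assumed to be approximately 66 months", and concludes that "it is calculated that a total of 504 deaths need to be observed". The looks are at 63, 83 and 100% information with Lan-DeMets O'Brien-Fleming spending. SAP 3.2 repeats the 80% and the 504 deaths. No DFS term enters either calculation.

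Protocol 10.5.1, 10.7.2 and 10.9 all say that OS is tested only if DFS is significant. Section 10.7.2 puts the first OS look at the final DFS analysis, "at which point a total of approximately 318 (63%) deaths are expected". Table 10-2 gives DFS power of 89.56% and cumulative OS power of 36.26, 64.09 and 79.25%, with footnote "b: Power conditional on DFS being significant". The table in SAP 2.13.2 has the same figures and footnote.

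The projected times (months 42, 52 and 63) rest on 1500 subjects at 50 per month. The Amendment 03 rationale states: "A total of 1382 subjects were randomized, which is less than 1500 subjects originally planned".

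**The concern.** A stand-alone power, a power conditional on DFS success and a joint probability of DFS and OS success are three different quantities. The table prints the first and labels it as the second. The third, which is the chance that the trial ends with a formal OS claim, appears nowhere.

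A reader can go wrong in either direction. Taking 10.9 at face value suggests an 80% chance of an OS claim. Taking the footnote at face value and multiplying by DFS power gives 0.8956 × 0.7925 = 71.0%. Neither is what the design delivers unless a particular correlation happens to hold. What is at stake is an accurate statement of what the testing sequence can achieve. Error control is not in question, because the boundaries are derived from the deaths actually observed.

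**Working it through.** **Inputs.** OS: HR 0.776, placebo median 66 months, 504 deaths, looks at 318/418/504, one-sided 2.5%, 1:1 allocation, 3% yearly loss (10.9). DFS: placebo median 48 months, HR 0.716, 392 events, 5% yearly dropout (10.8); futility Z 0.226 at 196 events and final Z 1.969 (10.7.1). Accrual: 50 per month for 30 months (10.8). The DFS–OS correlation is not given, so it is varied from 0 to 1.

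**1. Reproduce the first-look deaths.** With exponential survival, uniform accrual over A = 30 months and dropout hazard d, expected deaths per arm at month T are 750 × h/(h+d) × {1 − [e^(−(h+d)(T−A)) − e^(−(h+d)T)] / [(h+d)A]}.
- Placebo h = ln 2/66 = 0.01050; canakinumab h = 0.776 × 0.01050 = 0.00815; d = −ln(0.97)/12 = 0.00254.
- At T = 42 this gives about 176.5 + 141.5, or 318 deaths. At months 52 and 63 it gives 414 and 507, against 418 and 504 stated. The plan's projection reproduces.

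**2. Reproduce the OS powers with DFS ignored.** Spending function: 2[1 − Φ(2.241/√t)]. Boundaries at 318/418/504 deaths: Z = 2.592, 2.244, 2.041. The mean of Z is √(D/4) × |ln 0.776| = √(D/4) × 0.2536.
- First look: √79.5 × 0.2536 = 2.261, so power = 1 − Φ(2.592 − 2.261) = 37.1%.
- Cumulative over three looks: 37.1, 64.5 and 80.2%. The Freedman form gives 36.6, 64.0 and 79.8%.
- Printed: 36.26, 64.09 and 79.25%. The table is the stand-alone OS design.

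**3. Add the DFS requirement.** DFS succeeds if Z ≥ 0.226 at 196 events and Z > 1.969 at 392. At HR 0.716 this has probability 90.5% (stated: 89.56% simulated, 90.4% in text). Let r be the correlation between the final DFS statistic and the first-look OS statistic. By the final OS look:

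| r | DFS and OS both significant | OS significant, given DFS significant |
|---|---|---|
| 0 | 72.6% | 80.2% |
| 0.5 | 75.0% | 82.8% |
| 0.7 | 76.2% | 84.2% |
| 0.9 | 77.6% | 85.7% |
| 1 | 78.3% | 86.6% |

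A patient-level check (3,000 trials, both endpoints exponential as stated, DFS the earlier of recurrence and death) gave r of about 0.84, joint probability 77.3% and conditional power 86.2%.

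**4. Projections under the documented accrual.** The amendment rationales give 63 randomised by 11-Dec-2018, 507 by 05-Feb-2020, 1234 at the 01-Sep-2021 safety cut-off and 1382 in total. The first and last randomisation dates are not given; March 2018 and about January 2022 are assumed. With the planned hazards, 392 DFS events fall near month 57, still with about 318 deaths. Deaths 418 and 504 fall near months 69 and 80, against 52 and 63 in the plan. The death count at the DFS analysis hardly moves because both endpoints slow together.

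**5. Observed DFS pace.** The same accrual and planned hazards project about 137 DFS events by 01-Feb-2021; Amendment 03 records 201. Matching 201 needs DFS hazards about 1.55 times plan. If OS hazards rise by the same factor, deaths at 392 DFS events are again about 318. If OS hazards stay at plan, they are about 218: 218/504 = 43% information and about 9% first-look power.

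**The case against.** The plan never presents 80% as the joint probability. Section 10.9 opens by making OS testing depend on DFS, the table footnotes repeat it, and DFS power stands in the same table. This is fair: the 80% is not miscalculated, and the gap is an omission. The label also errs on the cautious side, since true conditional power is at or above the printed value for any non-negative correlation. And the joint figure needs a correlation that the documents do not supply. That calls for a range, but does not rescue 80%: even at r = 1 the joint probability is 78.3%.

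A reader might go further and infer that the 318 deaths and 36% first-look power are wrong, or that the first look really has about 9% power. The documents do not support that. Both printed figures reproduce from the stated inputs, and the smaller, slower accrual alone leaves deaths at about 318. The 218-death case needs DFS hazards to run ahead of plan while OS hazards do not, and no pooled death count is given to show this. The number randomised at 01-Feb-2021 is also interpolated.

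A related argument is that two separate exponentials imply 48/66 = 73% of early placebo DFS events are deaths without recurrence. Assuming a share of 5–30% instead, with the OS medians kept, gives about 221–247 deaths at month 42 and 10–16% power. That share is not in the documents either, so this too is only a sensitivity analysis.

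Finally, SAP 3.2 already ties boundaries to actual events, and the close-out SAP records that the primary endpoint was not met, so OS was not formally tested. This limits the practical consequence but does not correct the label.

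**Conclusion.** The point holds in a limited form. The OS powers in both tables are stand-alone figures carrying the wrong label. The probability of a formal OS success is about 73% (independence) to 78% (perfect correlation), roughly 2 to 7 percentage points below 80%, and is not stated. True conditional power at the final look is about 83–87% for correlations of 0.5 to 1; it equals the stand-alone value only under independence, which is implausible because deaths count as DFS events. These results assume the plan's own hazard ratios, event counts and boundaries, with the correlation as the one added assumption.

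The month and sample-size projections are out of date: 1382 subjects were randomised rather than 1500, and the SAP document history itself attributes unreliable timings to slow enrolment. The 318 deaths and 36% are not an error. DFS events running ahead of projection is a reason to check them, not evidence that they are wrong. Type I error is unaffected.

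**What to change.** - In Table 10-2 and the SAP 2.13.2 table, reword footnote b to say stand-alone OS power, without regard to the DFS result.
- In protocol 10.9, Table 10-2, SAP 2.13.2 and SAP 3.2, add the joint probability of DFS and OS success as a range over a stated DFS–OS correlation (72.6% at 0, 75.0% at 0.5, 78.3% at 1 by the final look).
- Update the projections that rest on 1500 subjects at 50 per month (protocol 4.2, 10.7.2, Table 10-2, 10.8 and 10.9; SAP 2.13.2 and 3.1) to 1382 subjects and the actual accrual.
- Check 318 deaths and 36% against the blinded pooled death count. If the case of 218 deaths, 43% information and about 9% power is shown, present it as a sensitivity case with its assumption stated: OS hazards at plan, DFS hazards about 1.55 times plan.

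The cost is slightly less favourable stated figures. Boundaries, event targets and enrolment stay as they are.
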